8.10.2. Visit 2: 1-Month Follow-up Visit (28-35 Days After Visit 1)

- Review the participant's e-diary data and collect the e-diary. Collect stop dates of any
 e-diary events ongoing on the last day that the e-diary was completed and record stop
 dates in the CRF if required.
- Confirm understanding of and compliance with protocol requirements for contraception.
- Perform a urine pregnancy test for female participants of childbearing potential.
- Ensure and document that the participant is still eligible for the study.
- Collect a blood sample of approximately 50 mL for antibody assessment.
- Collect and record nonstudy vaccinations as described in Section 6.5.4.
- Collect and record AEs (including MAEs) and SAEs, as described in Section 8.3.1.
- Complete the source documents.
- The investigator or an authorized designee completes the CRFs.

8.10.3. Unscheduled Reactogenicity Visits

If the participant reports 1 or more of the following, a contact **must** occur as soon as possible between the participant and the investigator, or a medically qualified member of the study site staff, to assess if an unscheduled visit is required.

- redness at the injection site on the left arm measuring >20 measuring device units (>10.0 cm),
- swelling at the injection site on the left arm measuring >20 measuring device units (>10.0 cm),
- severe injection site pain on the left arm,
- fever ≥ 39.0 °C (≥ 102.1 °F).

A site visit should be scheduled as soon as possible to assess the extent of the reaction unless:

- The participant is unable to attend the unscheduled visit, or
- The reaction is no longer present at the time of the contact, or
- The participant recorded an incorrect value in the e-diary (confirmation of an e-diary data entry error), or
- The investigator determines that the visit is not required.

This contact will be recorded in the participant's source notes and in the CRF.

If the participant is unable to attend the unscheduled visit, any ongoing reactions must be assessed at the next scheduled visit.

The reactogenicity events should be assessed by the investigator or a medically qualified member of the site staff such as a study physician or a study nurse, as applicable to the investigator's local practice, who will:

- Measure oral temperature.
- Measure the participant's heart rate.
- Measure the participant's blood pressure (seated).
- Measure the minimum and maximum diameters of redness on the left arm (if present).
- Measure the minimum and maximum diameters of swelling on the left arm (if present).
- Assess any necrosis at the injection site on the left arm.
- Assess any exfoliative dermatitis.
- Assess any injection site pain on the left arm that is present in accordance with the reactogenicity grading scale provided in Section 8.2.2.
- Assess any systemic events (fatigue, headache, nausea, vomiting, diarrhea, muscle pain, or joint pain) that are present in accordance with the reactogenicity grading scale provided in Section 8.2.3.
- Ask the participant if she attended an emergency room visit or was hospitalized.
- For severe pain at the injection site on the left arm associated with an emergency room visit or hospitalization, severe systemic events associated with an emergency room visit or hospitalization, or any necrosis on the left arm or exfoliative dermatitis, the

investigator must assess these events in accordance with the intensity AE grading scale provided in Section 8.2.2 and Section 8.2.3 for documentation on the AE CRF.

- Collect and record AEs (including MAEs) and SAEs as described in Section 8.3.1 and complete the source documents.
- The investigator or an authorized designee will complete the CRFs.

Participants will be instructed to contact the site to report any significant illness, medically attended event, or hospitalization that occurs during the study period. Study staff may contact the participant to obtain additional information on Grade 3 events entered into the e-diary.

9. STATISTICAL CONSIDERATIONS

Methodology for summary and statistical analyses of the data collected in this study is outlined here and further detailed in a SAP, which will be maintained by the sponsor. The SAP may modify what is outlined in the protocol where appropriate; however, any major modifications of the primary endpoint definitions or their analyses will also be reflected in a protocol amendment.

9.1. Estimands and Statistical Hypotheses

The null hypothesis (H_0) for assessing noninferiority with respect to the antipertussis immunogenicity endpoints is:

$$H_0$$
: $\ln(\mu_1) - \ln(\mu_2) \le -\ln(1.5)$

where $ln(\mu_1)$ is the mean of the natural logarithm-transformed antibody concentration at 1 month after vaccination from participants in the combined RSV vaccine + Tdap groups, and $ln(\mu_2)$ is the mean of the natural logarithm-transformed antibody concentration from participants in the placebo + Tdap group. The antibody concentration data will be logarithmically transformed for analysis of GMC ratios along with 95% confidence intervals (CIs), and results will be presented on the original scale.

The H_0 for assessing noninferiority with respect to the RSV immunogenicity endpoints is:

$$H_0$$
: $ln(\mu_1)-ln(\mu_3) \le -ln(2)$

where $ln(\mu_1)$ is the mean of the natural logarithm-transformed antibody titer at 1 month after vaccination from participants in the combined RSV vaccine + Tdap groups, and $ln(\mu_3)$ is the mean of the natural logarithm-transformed antibody titer from participants in the combined RSV vaccine + placebo groups. The antibody titer data will be logarithmically transformed for analysis of GMT ratios along with 95% CIs, and results will be presented on the original scale.

The H₀ for assessing noninferiority for binary antidiphtheria and antitetanus immunogenicity endpoints is:

$$H_0$$
: $\pi 1 - \pi 2 \le -10\%$

where π_1 and π_2 are the percentages of participants with antibody concentrations above certain thresholds at 1 month after vaccination for the combined RSV vaccine + Tdap groups and the placebo + Tdap group, respectively.

The noninferiority of RSV vaccine + Tdap to Tdap alone with respect to Tdap immune response will be evaluated at 1 month after vaccination for anti-TTd and anti-DTd antibodies and antipertussis components (anti-PT, anti-FHA, and anti-PRN). The primary objective of noninferiority will be met if

- The lower bound of the 2-sided 95% CI for the difference (combined RSV vaccine + Tdap groups minus placebo + Tdap group) in the percentage of participants with antitetanus concentrations ≥0.1 IU/mL is > the predefined limit of -10% (noninferiority margin of 10%); and
- The lower bound of the 2-sided 95% CI for the difference (combined RSV vaccine + Tdap groups minus placebo + Tdap group) in the percentage of participants with antidiphtheria concentrations ≥0.1 IU/mL is > the predefined limit of -10%; and
- The lower bound of the 2-sided 95% CI for the GMC ratio (combined RSV vaccine + Tdap groups divided by placebo + Tdap group) is > the predefined limit of 0.67 (noninferiority margin of 1.5-fold) for each pertussis antigen (PT, FHA, and PRN).

The noninferiority of RSV vaccine + Tdap to RSV vaccine alone with respect to RSV immune response will be evaluated at 1 month after vaccination for RSV A– and RSV B– neutralizing antibody titers. The primary objective of noninferiority will be met if

• The lower bounds of the 2-sided 95% CI for the GMT ratio (combined RSV vaccine + Tdap groups divided by combined RSV vaccine + placebo groups) are > the predefined limit of 0.5 (noninferiority margin of 2-fold) for RSV A– and RSV B– neutralizing antibodies.

The primary hypotheses for Tdap antibody endpoints and the primary hypotheses for RSV A– and RSV B–neutralizing antibody endpoints will be tested simultaneously. The 2 primary objectives of noninferiority will be met only if all statistical criteria for both objectives are met. Therefore, the multiplicity of primary objectives does not require an alpha adjustment.

Conditional upon success of the primary objective for RSV responses, the secondary objective of noninferiority relative to a more stringent margin will be tested. The secondary objective will be met if the lower bounds of the 2-sided 95% CI for the GMT ratio (combined RSV vaccine + Tdap groups divided by combined RSV vaccine + placebo groups) are > the

predefined limit of 0.67 (noninferiority margin of 1.5-fold) for RSV A– and RSV B–neutralizing antibodies.

9.1.1. Estimands

Immunogenicity:

In participants receiving at least 1 dose of investigational product and in compliance with the key protocol criteria (evaluable participants):

- The difference in percentage of participants with anti-TTd antibody concentrations ≥0.1 IU/mL between the combined RSV vaccine + Tdap groups and the placebo + Tdap group
- The difference in percentage of participants with anti-DTd antibody concentrations ≥0.1 IU/mL between the combined RSV vaccine + Tdap groups and the placebo + Tdap group
- GMC ratio, estimated by the ratio of the GMC of anti-PT antibodies from the combined RSV vaccine + Tdap groups to the placebo + Tdap group
- GMC ratio, estimated by the ratio of the GMC of anti-FHA antibodies from the combined RSV vaccine + Tdap groups to the placebo + Tdap group
- GMC ratio, estimated by the ratio of the GMC of anti-PRN antibodies from the combined RSV vaccine + Tdap groups to the placebo + Tdap group
- GMT ratio, estimated by the ratio of the GMT for RSV A– and RSV B–neutralizing antibody titers from the combined RSV vaccine + Tdap groups to the combined RSV vaccine + placebo groups.

These estimands estimate the vaccine effect in the hypothetical setting where participants follow the study schedules and protocol requirements as directed. Missing serology results will not be imputed, as missing completely at random (MCAR) is assumed. For participants who discontinue from the study or have major protocol violations, all postdiscontinuation or violation observations will be censored.

Safety:

In participants receiving at least 1 dose of investigational product:

- The percentage of participants reporting local reactions.
- The percentage of participants reporting systemic events.
- The percentage of participants reporting AEs.

• The percentage of participants reporting MAEs and SAEs.

Missing e-diary data will not be imputed; missing AE dates and missing AE severity will be handled according to Pfizer safety rules.

9.2. Sample Size Determination

The study has 2 primary immunogenicity objectives. The study sample size is based upon the evaluation of noninferiority of RSV vaccine coadministration with Tdap to Tdap alone or to RSV vaccine alone on 7 coprimary endpoints. For the continuous immunogenicity endpoints, ie, GMC/GMT ratio, noninferiority will be evaluated using a 2-fold margin as the criterion for RSV endpoints, and a 1.5-fold margin as the criterion for pertussis endpoints. A 10% margin will be used to evaluate noninferiority for the binary immunogenicity endpoints. It was assumed that there was no inherent difference between the 2 groups (ie, a GMC/GMT ratio of 1 for the continuous endpoints and a difference of 0% for the binary endpoints).

Table 5 presents the power to demonstrate noninferiority, for the 2 RSV vaccine formulations combined. The power calculations were performed using PROC POWER in SAS 9.4. With 128 evaluable participants in each group, the study will have 92.2% power to demonstrate noninferiority of the combined RSV vaccine formulations coadministered with Tdap to Tdap alone with respect to GMC of antipertussis components (anti-PT, anti-FHA, and anti-PRN), and have >99.9% power to demonstrate noninferiority of the combined RSV vaccine formulations coadministered with Tdap to RSV vaccine alone with respect to GMT of RSV A− and RSV B−neutralizing antibody titers. The study will also have 99.9% power to demonstrate noninferiority of the combined RSV vaccine formulations coadministered with Tdap to Tdap alone with respect to the percentage of participants with antitetanus and antidiphtheria antibody concentrations ≥0.1 IU/mL. The overall power to demonstrate noninferiority on all 7 primary endpoints is 92.1%.

Assuming a nonevaluable rate of 10%, the study will randomize up to approximately 710 participants to achieve 128 evaluable participants in each group.

Table 5. Power to Show Noninferiority of Combined RSV Vaccine Formulations Administered With Tdap (RSV + Tdap) to Tdap Alone (Placebo + Tdap) and RSV Vaccine Alone

Endpoint	% in Placebo	Assumed % in	NI Margin ^b	N Evaluab	ole/Group	Power ^c
	+ Tdap	RSV + Tdap		Placebo +	RSV +	
	Group ^a	Group		Tdap	Tdap	
Anti-TTd	97.4%	97.4%	10%	128	256	99.9%
Anti-DTd	98.3%	98.3%	10%	128	256	>99.9%
Power to show NI for both anti-TTd and anti-DTd				99.9%		

Table 5. Power to Show Noninferiority of Combined RSV Vaccine Formulations Administered With Tdap (RSV + Tdap) to Tdap Alone (Placebo + Tdap) and RSV Vaccine Alone

Endpoint	Standard	Assumed GMC	NI Margin ^d	N Evaluable/Group		Power ^c
_	Deviation (ln) ^a	Ratio		Placebo +	RSV +	
				Tdap	Tdap	
Anti-PT	0.967	1	1.5-fold	128	256	97.2%
Anti-FHA	0.737	1	1.5-fold	128	256	99.8%
Anti-PRN	1.036	1	1.5-fold	128	256	95.0%
Power to show NI for anti-PT, anti-FHA, and anti-PRN					92.2%	
Endpoint	Standard	Assumed GMC	NI Margin ^e	N Evaluat	ole/Group	Power ^c
-	Deviation (ln) ^a	Ratio		RSV +	RSV +	
				Placebo	Tdap	
RSV A	1.002	1	2-fold	256	256	>99.9%
RSV B	1.087	1	2-fold	256	256	>99.9%
Power to show NI for both RSV A and RSV B					>99.9%	
Power to show NI for all 7 primary endpoints				92.1%		

Abbreviations: anti-DTd = anti-diphtheria toxoid; anti-TTd = anti-tetanus toxoid; FHA = filamentous hemagglutinin; GMC = geometric mean concentration; NI = noninferiority; PRN = pertactin; PT = pertussis toxin

- a. Reference study B1971015 (Tdap endpoints); C3671001 sentinel cohort (RSV vaccine endpoints).
- b. NI met if lower limit of 95% CI for the difference (RSV+Tdap placebo+Tdap) > -10%.
- c. At 0.05 alpha level (2-sided).
- d. NI met if lower limit of 95% CI for the GMC ratio [(RSV+Tdap)/(placebo+Tdap)] > 0.67.
- e. NI met if lower limit of 95% CI for the GMT ratio [(RSV+Tdap)/(RSV+placebo)] > 0.5.

For the sample size of 710 randomized participants, Table 6 presents the power to demonstrate noninferiority for an individual RSV vaccine formulation. The power calculations were performed using PROC POWER in SAS 9.4. With 128 evaluable participants in each group, the study will have 79.3% power to demonstrate noninferiority of an individual RSV vaccine formulation coadministered with Tdap to Tdap alone with respect to the GMC of antipertussis components (anti-PT, anti-FHA, and anti-PRN), and have 99.9% power to demonstrate noninferiority of an individual RSV vaccine formulation coadministered with Tdap to RSV vaccine alone with respect to the GMT of RSV A− and RSV B−neutralizing antibody titers. The study will also have 97.8% power to demonstrate noninferiority of an individual RSV vaccine formulation coadministered with Tdap to Tdap alone with respect to the percentage of participants with antitetanus and antidiphtheria antibody concentrations ≥0.1 IU/mL. The overall power to demonstrate noninferiority on all 7 primary endpoints is 77.5%.

Table 6. Power to Show Noninferiority of Individual RSV Vaccine Formulations Administered With Tdap (RSV + Tdap) to Tdap Alone (Placebo + Tdap) and RSV Vaccine Alone

Endpoint	% in Placebo	Assumed % in	NI Margin ^b	N Evaluab	ole/Group	Power ^c
_	+ Tdap	RSV + Tdap		Placebo +	RSV +]
	Group ^a	Group		Tdap	Tdap	
Anti-TTd	97.4%	97.4%	10%	128	128	98.1%
Anti-DTd	98.3%	98.3%	10%	128	128	99.7%
Power to show	w NI for both ant	i-TTd and anti-D	Γd			97.8%
Endpoint	Standard	Assumed GMC	NI Margin ^d	N Evaluab	ole/Group	Power ^c
_	Deviation (ln) ^a	Ratio		Placebo +	RSV +	
				Tdap	Tdap	
Anti-PT	0.967	1	1.5-fold	128	128	91.7%
Anti-FHA	0.737	1	1.5-fold	128	128	98.5%
Anti-PRN	1.036	1	1.5-fold	128	128	87.8%
Power to show	w NI for anti-PT,	anti-FHA, and an	ti-PRN			79.3%
Endpoint	Standard	Assumed GMC	NI Margin ^e	N Evaluab	ole/Group	Power ^c
_	Deviation (ln) ^a	Ratio		RSV +	RSV +]
				Placebo	Tdap	
RSV A	1.002	1	2-fold	128	128	>99.9%
RSV B	1.087	1	2-fold	128	128	99.9%
Power to show NI for both RSV A and RSV B			99.9%			
Power to show	w NI for all 7 prii	nary endpoints				77.5%

Abbreviations: anti-DTd = anti-diphtheria toxoid; anti-TTd = anti-tetanus toxoid; FHA = filamentous hemagglutinin; GMC = geometric mean concentration; GMT = geometric mean titer; NI = noninferiority; PRN = pertactin; PT = pertussis toxin.

- a. Reference study B1971015 (Tdap endpoints); C3671001 sentinel cohort (RSV vaccine endpoints).
- b. NI met if lower limit of 95% CI for the difference (RSV+Tdap placebo+Tdap) > -10%.
- c. At 0.05 alpha level (2-sided).
- d. NI met if lower limit of 95% CI for the GMC ratio [(RSV+Tdap)/(placebo+Tdap)] > 0.67.
- e. NI met if lower limit of 95% CI for the GMT ratio [(RSV+Tdap)/(RSV+placebo)] > 0.5.

The sample size of 710 also allows for at least 90% overall power, if the noninferiority margin of 1.5 applies to the RSV responses, as in the secondary objective. Table 7 summarizes the power for the secondary objective and the power for the overall test of noninferiority including the 1.5-fold margin for the RSV responses.

Table 7. Power to Show Noninferiority of Combined RSV Vaccine Formulations
Administered With Tdap (RSV + Tdap) to Tdap Alone (Placebo + Tdap)
and RSV Vaccine Alone, Using 1.5-Fold Margin for RSV Responses

Endpoint	Standard	Assumed GMC	NI Margin ^b	N Evaluable/Group		Power ^c
	Deviation (ln) ^a	Ratio		RSV +	RSV +	
				Placebo	Tdap	
RSV A	1.002	1	1.5-fold	256	256	99.5%
RSV B	1.087	1	1.5-fold	256	256	98.8%
Power to show NI for both RSV A and RSV B				98.3%		
Power to show NI for RSV responses and all Tdap responses (per primary endpoints)				90.5%		

Abbreviations: GMC = geometric mean concentration; GMT = geometric mean titer; NI = noninferiority.

- a. Reference study C3671001 sentinel cohort.
- b. NI met if lower limit of 95% CI for the GMT ratio [(RSV+Tdap)/(RSV+placebo)] > 0.67.
- c. At 0.05 alpha level (2-sided).

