9.4.1. Immunogenicity Analyses

Endpoint	Statistical Analysis Methods
Primary	The 95% CIs for the difference (RSV vaccine + Tdap group minus placebo + Tdap group) in the percentage of participants with antitetanus and antidiphtheria concentrations ≥0.1 IU/mL will be calculated using the Miettinen and Nurminen method.

Endpoint	Statistical Analysis Methods
	• Geometric mean ratios (GMRs) of the RSV vaccine + Tdap group to the placebo + Tdap group for the anti-PT, anti-FHA, and anti-PRN antibody at 1 month after vaccination will be calculated, along with associated 2-sided 95% CIs. The GMR will be calculated as the group mean difference of logarithmically transformed antibody levels and transformed back to the original units. Two (2)-sided 95% CIs will also be obtained by calculating CIs using a 2-sample Student's t distribution for the mean difference of measures on the logarithmically transformed assay results, and transforming confidence limits back to the original units.
	GMRs of the RSV vaccine + Tdap group to the RSV vaccine + placebo group for the RSV A- and RSV B-neutralizing antibody titers at 1 month after vaccination will be calculated, along with associated 2-sided 95% CIs, using the same method as for anti-PT, anti-FHA, and anti-PRN antibody GMRs.
	Titers below the lower limit of quantitation (LLOQ) or denoted as below the limit of quantitation (BLQ) will be set to 0.5 × LLOQ for GMT/GMC analysis.
	This analysis is based on the evaluable population in order to provide a comparison of the 2 groups that has the greatest chance of identifying a difference between the groups with respect to immunogenicity, if a meaningful difference actually exists (ie, results of the comparisons fail to establish noninferiority). An additional analysis will be performed based on the mITT population if there is enough difference between the mITT population and the evaluable population. Participants will be summarized according to the vaccine group to which they were randomized. Missing serology data will not be imputed.
CCI	

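### The anti-FHA powers in Tables 5 and 6 (99.8% and 98.5%) do not follow from the printed SD of 0.737 under the stated noninferiority criterion, which gives 99.9% and 99.2%

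*Protocol*

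**What the plan says.** Protocol section 9.2 gives the anti-FHA row twice. Table 5 (combined formulations) has "Anti-FHA 0.737 1 1.5-fold 128 256 99.8" and Table 6 (one formulation) has "Anti-FHA 0.737 1 1.5-fold 128 128 98.5". The columns are SD on the ln scale, assumed ratio, margin, evaluable n in each group, and power in percent.

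The other inputs are fixed nearby:
- The text of section 9.2 sets "a 1.5-fold margin as the criterion for pertussis endpoints" and assumes "a GMC/GMT ratio of 1 for the continuous endpoints and a difference of 0% for the binary endpoints".
- Footnote c of both tables reads "At 0.05 alpha level (2-sided").
- Footnote d reads "NI met if lower limit of 95% CI for the GMC ratio [(RSV+Tdap)/(placebo+Tdap)] > 0.67", so only the lower limit counts.
- Section 9.4.1 obtains the interval "using a 2-sample Student's t distribution for the mean difference of measures on the logarithmically transformed assay results".

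The text names PROC POWER in SAS 9.4 but not the test option. The Table 6 joint figure is repeated in the text: "With 128 evaluable participants in each group, the study will have 79.3% power to demonstrate noninferiority of an individual RSV vaccine formulation".

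**The concern.** A power table should reproduce from its own row. The anti-FHA rows do not, while their neighbours do. Anti-FHA is one of the seven coprimary endpoints, and the joint powers are products of the printed rows, so a wrong row carries into the totals. A reader also cannot tell whether the row was run with a different test from the rest or with an SD other than the one printed.

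Little is at stake in percentage points. Near 100%, though, the more telling scale is the chance of missing noninferiority. In Table 6 the printed chance for anti-FHA is 1.5%, against 0.77% from the printed inputs, or about double.

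**Working it through.** **Inputs** (protocol sections 9.2 and 9.4.1): ln-scale SD 0.737; true ratio 1; margin ln(1.5) = 0.4055; one-sided alpha 0.025, which is the lower limit of a two-sided 95% interval; evaluable n 128 versus 128 (Table 6) and 128 versus 256 (Table 5). The 10% nonevaluable rate plays no part, because the tables use evaluable n.

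**Formula.** SE = SD × √(1/n1 + 1/n2). Noncentrality = 0.4055 / SE. Power = P(noncentral t > t at 0.975), with n1 + n2 − 2 degrees of freedom.

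**Step 1. The method reproduces the other continuous rows.**

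| Row | n | Computed | Printed |
|---|---|---|---|
| Anti-PT, SD 0.967 | 128/128 | 91.65% | 91.7% |
| Anti-PT | 128/256 | 97.15% | 97.2% |
| Anti-PRN, SD 1.036 | 128/128 | 87.68% | 87.8% |
| Anti-PRN | 128/256 | 95.01% | 95.0% |
| RSV A, SD 1.002, 1.5-fold | 256/256 | 99.55% | 99.5% |
| RSV B, SD 1.087, 1.5-fold | 256/256 | 98.78% | 98.8% |

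The largest gap is about 0.1 point.

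**Step 2. Anti-FHA by the same method.**
- 128/128: SE = 0.737 × √(2/128) = 0.0921; noncentrality 4.40; power 99.23%, printed 98.5%.
- 128/256: SE = 0.737 × √(1/128 + 1/256) = 0.0798; noncentrality 5.08; power 99.91%, printed 99.8%.

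The normal approximation gives 99.27% and 99.91%. Using the rounded limit 0.67 as the margin gives 99.11% and 99.88%. Neither gives the printed pair.

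**Step 3. What would give the printed values.**

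*(a) Two one-sided equivalence tests (TOST) at 0.025 per side, SD 0.737.* With a true ratio of 1 and symmetric margins, the miss risk doubles, so power is 2 × (one-sided power) − 1:
- 128/128: 2 × 99.234% − 100% = 98.47%, which rounds to the printed 98.5%.
- 128/256: 2 × 99.906% − 100% = 99.81%, which rounds to the printed 99.8%.

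At 128/128 the same option gives 83.3% for anti-PT and 75.4% for anti-PRN, far from the printed 91.7% and 87.8%. It could therefore apply only to the anti-FHA row.

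*(b) One-sided noninferiority with another SD.* Powers that round to 98.5% at 128/128 need an SD of 0.780 to 0.785. Powers that round to 99.8% at 128/256 need 0.758 to 0.784. An SD of about 0.780 to 0.784 satisfies both.

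**Step 4. Effect on the totals if 0.737 is right.** The plan's own totals are products of its printed rows: 0.917 × 0.985 × 0.878 = 0.793 and 0.972 × 0.998 × 0.950 = 0.922. With all three pertussis rows recomputed, and the printed powers kept for the other endpoints:

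| Total | Calculation | Result | Printed |
|---|---|---|---|
| Table 6 pertussis | 0.9165 × 0.9923 × 0.8768 | 79.7% | 79.3% |
| Table 6 all 7 | 0.7974 × 0.978 × 0.999 | 77.9% | 77.5% |
| Table 5 pertussis | 0.9715 × 0.9991 × 0.9502 | 92.2% | 92.2% |
| Table 5 all 7 | 0.9222 × 0.999 | 92.1% | 92.1% |
| Table 7 overall | 0.9222 × 0.999 × 0.983 | 90.6% | 90.5% |

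The last digit depends on rounding. Keeping the printed anti-PT and anti-PRN powers and replacing only anti-FHA by its rounded value gives 0.917 × 0.992 × 0.878 = 79.9% for Table 6 pertussis power. For Table 5 all-7 power it gives 92.16% instead of the unrounded 92.13%.

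**The case against.** The strongest reply is that the printed SD does give both printed powers, to the decimal, under the equivalence option, and that the protocol never states which PROC POWER option was used. This part stands: a misprinted SD is not established. A reader might infer that the true SD is about 0.78 and that the assumption in both tables is about 6% too low. The documents do not support that. The value 0.78 appears nowhere in them, and the reference study is not available to check.

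The reply does not rescue the printed powers, however. Both tables are titled as power to show noninferiority, footnote d uses the lower limit only, and the neighbouring rows follow that test. For the stated criterion, 98.5% and 99.8% are not what SD 0.737 gives.

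A second reply is that 0.1 and 0.7 points are negligible and would pass a tolerance of 2 points. For Table 5, which supports the sample size, the gap is indeed no larger than the gap accepted for anti-PRN in Table 6. But the tables print one decimal and the other rows agree to about 0.1 point, so the Table 6 gap is not rounding.

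It is also fair to say that Table 6 concerns a single formulation and carries no decision rule, since the primary hypotheses in section 9.1 use the combined groups. That limits the weight of the point but does not remove it.

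**Conclusion.** The point holds as a small reporting error. Under the noninferiority criterion in footnote d, the printed anti-FHA inputs give 99.9% (Table 5) and 99.2% (Table 6), not 99.8% and 98.5%. Either the row was run with a different test option from its neighbours, or a different SD was used; the documents cannot settle which.

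The error is conservative, because printed power is below computed power. If 0.737 is right, the two Table 6 totals rise by about 0.4 point and the Table 7 overall figure by 0.1 point. A reader might infer that the joint power behind the sample size is wrong; it is not, because Table 5's 92.2% and 92.1% are unchanged. Sample size, margins, analysis and conduct are unaffected.

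This rests on a one-sided 0.025 two-sample t test with a common SD, a true ratio of 1, and joint power taken as the product of the components, as the plan's own totals are.

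**What to change.** Retrieve the anti-FHA PROC POWER run, and check its test option and its SD against reference study B1971015.

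- If 0.737 is right, restate anti-FHA power as 99.9% (Table 5) and 99.2% (Table 6). Restate Table 6 pertussis power as 79.7% and all-7 power as 77.9%, in the table and in the text of section 9.2, and Table 7 overall as 90.6%. Leave Table 5's joint 92.2% and overall 92.1% as they are. Take final decimals from unrounded output.
- If a different SD was used, print that SD in both tables; the powers and totals then stay as printed.

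In either case, state the PROC POWER test option once in section 9.2. The cost is one rerun and a few corrected figures, with no change to size or conduct.
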